13.2 Adjustment for Covariates

Not applicable.

13.3 Handling of Missing Data

Missing data imputation rules are described in [Section 5.2](#).

13.4 Multiple Comparisons / Multiplicity

No hypothesis testing is planned.

14. METHODS OF EFFICACY ANALYSES

14.1 Analysis of Continuous Efficacy Endpoints

Descriptive statistics for all efficacy endpoints listed in [Section 13.1](#) will be tabulated by analysis visit (see [Section 5.6](#)). The summaries of observed values and change from baseline results will be presented.

15. SAFETY ANALYSES

All safety analyses will be performed using the Safety Analysis Set. Safety summaries will be presented using descriptive statistics. For each continuous measure in clinical laboratory variables, vital signs, and electrocardiogram, change from baseline results will be displayed by analysis visit.

15.1 Primary Safety Endpoints

The primary safety endpoints are:

- Treatment-emergent adverse events (TEAEs)
- Serious adverse events (SAEs)
- Withdrawals due to adverse events (AEs)
- Potentially clinically important changes in other safety assessments

15.2 Adverse Events

Adverse events will be coded using MedDRA dictionary version 24.0.

An AE (classified by preferred term) will be considered a treatment-emergent AE (TEAE) if started after first dose administration and no later than last dose date + 30 days.

The event counts, the number, and percentage of subjects reporting TEAEs will be tabulated by system organ class (SOC) and PT; and by SOC, PT, and maximum severity. A subject is counted at most once per SOC and PT even if the subject has more than one TEAE. A subject is counted at most once per SOC and PT at the maximum severity for the summary by maximum severity. The display in these tables will be sorted alphabetically by SOC and then by descending subject frequency for the PTs within each SOC.

The event counts, the number and percentage of subjects with any TEAEs will also be tabulated by PT without SOCs. This table will be sorted by descending subject frequency.

Treatment-emergent SAEs, TEAEs leading to study drug withdrawn, and TEAEs related to study drug will be summarized by SOC and PT. The tables will be sorted alphabetically by SOC and then by descending subject frequency for the PTs within each SOC. In addition, the incidence of fatal treatment-emergent AEs (i.e., events that cause death) will be summarized separately by SOC and PT.

An AE listing by subject will display all events, including those which are not treatment-emergent, and will include the verbatim term in addition to the MedDRA SOC and PT. This listing will also include all relevant eCRF data associated with the event: date of onset, date

resolved, date of last dose, severity, frequency, outcome, relationship to study drug, and action taken with study drug. Separate listings will be presented for treatment-emergent SAEs, TEAEs leading to study drug withdrawn, fatal TEAEs (if any), and TEAEs related to COVID-19 infection.

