Serious AEs occurring after the study follow-up period (i.e., 30[+4] days after last dose of study drug) should be reported if in the judgment of the Investigator there is "a reasonable possibility" that the event may have been caused by the product.

SAEs should also be reported to the IRB/EC according to local regulations.

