9.5.2 Safety Analyses

Safety results will be summarized using descriptive statistics. Adverse events will be coded into standard terminology using the Medical Dictionary for Regulatory Activities (MedDRA). Treatment-emergent adverse events (TEAEs), TEAEs leading to discontinuation, TEAEs considered related to study drug, TEAEs by maximum severity, and serious adverse events (SAEs) reported after study medication start, will all be summarized.

Descriptive statistics for ECG, vital signs and weight, and clinical laboratory parameters, including changes from Baseline, will be tabulated by timepoint. Additionally, categorical analyses will be conducted on the incidence of subjects with prolonged QTc (QT interval of ECG corrected for heart rate) intervals and changes in QTc intervals in accordance with International Council for Harmonisation (ICH) guidelines.

Additional safety analysis details will be specified in the SAP.

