17.2 Examination of Subgroups for Adverse Events

In addition to the analysis specified in [Section 15.2](#), the following summaries will be performed for adverse events with onset during Treatment Period A:

- TEAEs with onset during Treatment Period A: by SOC and PT; by SOC, PT and maximum severity; by PT only
- Treatment-emergent SAEs with onset during Treatment Period A: by SOC and PT
- TEAEs with onset during Treatment Period A that lead to study drug withdrawn during Treatment Period A: by SOC and PT
- TEAEs with onset during Treatment Period A that are related to study drug: by SOC and PT
- Fatal TEAEs with onset during Treatment Period A: by SOC and PT

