20. CHANGES TO ANALYSES SPECIFIED IN PROTOCOL

No changes are made to the analyses specified in the protocol.

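### The protocol's SAE summary has no end date, but the SAP tabulates and separately lists only SAEs with onset within 30 days of last dose and declares no change.

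*SAP*

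**What the plan says.** **Protocol.** Section 9.5.2, and the synopsis in the same terms, names four summaries based on treatment-emergent events (overall, leading to discontinuation, drug-related, by maximum severity). For serious events it changes the term: "serious adverse events (SAEs) reported after study medication start, will all be summarized". Section 7.3 has adverse events recorded from consent to the end of safety follow-up. Section 7.4.2 has subjects followed for SAEs through that period, which it defines as 30(+4) days after last dose. It adds: "Serious AEs occurring after the study follow-up period (i.e., 30[+4] days after last dose of study drug) should be reported", on condition that the Investigator sees a reasonable possibility that the product caused the event.

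**SAP.** Section 15.1 names SAEs as a primary safety endpoint, separately from TEAEs. Under section 15.2 an event is treatment-emergent "if started after first dose administration and no later than last dose date + 30 days". The SAE table is restricted to that class: "Treatment-emergent SAEs, TEAEs leading to study drug withdrawn, and TEAEs related to study drug will be summarized by SOC and PT". So is the SAE listing: "Separate listings will be presented for treatment-emergent SAEs". The extra interim table in section 17.2 uses the same class: "Treatment-emergent SAEs with onset during Treatment Period A: by SOC and PT". A general by-subject AE listing covers every event, treatment-emergent or not. Section 20 states: "No changes are made to the analyses specified in the protocol".

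**The concern.** Safety is a primary objective and SAEs are one of its named endpoints. The protocol gives the SAE summary a starting point and no end. The SAP closes it at 30 days after last dose, which is shorter than the protocol's own SAE follow-up. Events that the protocol plans to collect can then be absent from the table that reports the endpoint, while the SAP tells the reader that nothing has changed.

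In a study of this size SAE counts will be small, so one uncounted event would visibly change the reported result.

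**Working it through.** The plan gives no figure to reproduce. The check compares what is collected with what is tabulated, then sizes one omitted event.

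**Step 1: windows, in days after last dose**
- End of SAE follow-up (protocol 7.4.2): 30 + 4 = day 34 at the latest.
- End of the treatment-emergent window (SAP 15.2): day 30.
- Difference: 34 − 30 = 4 days, that is days 31 to 34. This is the maximum; it shrinks if the follow-up contact takes place on day 30.

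**Step 2: where an SAE ends up, by onset**

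| Onset of SAE | Collected? | Within protocol 9.5.2 as worded? | In SAP SAE table and SAE listing? | In general AE listing? |
|---|---|---|---|---|
| After first dose, up to day 30 | Yes | Yes | Yes, whatever the report date | Yes |
| Timing unclear because the date is missing or partial | Yes | Yes, if reported after treatment start | Yes; SAP 5.9 treats it as treatment-emergent | Yes |
| Days 31 to 34 | Yes, while follow-up is open (7.3, 7.4.2) | Yes | **No** | Yes |
| After follow-up, judged possibly drug-related | Reporting recommended; entry to the clinical database not stated | Yes, if reported | **No** | Only if in the database |

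The third row is the firm part of the gap. The protocol uses its mandatory wording both for recording adverse events through follow-up and for following subjects for SAEs, and section 7.4.1 sends serious and non-serious events alike to the AE eCRF page. The fourth row is conditional.

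**Step 3: does any other SAP output fill the gap?** No further SAE table or SAE listing appears in SAP 15.2 or 17.2. The interim analysis reruns section 15, so the same limit applies there. The general AE listing shows the event as a row. Seriousness is not among the fields named for that listing, although it is to carry all relevant eCRF data.

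**Step 4: size of one omission.** Planned enrolment is about 10 to 15. If one subject's only SAE falls in the gap, incidence changes by 1/n:
- n = 15: 1/15 = 6.7 percentage points
- n = 10: 1/10 = 10.0 percentage points

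The documents give no rate from which to estimate how often this would happen.

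**The case against.** The best reply is that the protocol phrase only sets a lower bound. One is needed because adverse events are recorded from consent, and section 9.5.2 then leaves additional safety detail to the SAP, so a 30-day cut-off could be that detail. The endpoint label alone also proves little: withdrawals due to adverse events carries no qualifier either, yet section 9.5.2 itself turns it into a treatment-emergent summary. The label argument is therefore weak. The sentence in 9.5.2 is stronger evidence, because it uses the treatment-emergent term for four summaries and drops it only for SAEs. Adding detail does not extend to narrowing a stated summary while declaring no change.

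It is also fair to say that nothing is hidden, since the general AE listing shows every event and 10 to 15 subjects can be read by eye. That softens the consequence, but a listing row is not the promised summary.

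A reader might infer more than the documents support:
- **That late related SAEs must be reported and are then left uncounted in the database.** Section 7.4.2 says they should be reported, and the protocol's opening note defines that word as recommended, not required. SAEs go to the Sponsor on a paper form, and no text says that those arising after follow-up enter the clinical database.
- **That SAEs reported late are lost.** The SAP rule uses onset, so an SAE starting by day 30 counts whenever it is reported.
- **That the gap runs well past day 34.** Protocol Table S-2 times the contact from EOT/ET, so a 7-day delay between last dose and ET would extend the gap to day 41 (7 + 34). That delay is an assumption, and 7.4.2 counts from last dose.
- **That the fatal-event table breaks the protocol in the same way.** The protocol promises no such table; the SAP adds it.

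**Conclusion.** The mismatch is real and narrow. The SAP's SAE table and SAE listing cover less than protocol 9.5.2 describes, and SAP 20 does not disclose this. The firm part is onset on days 31 to 34, at most 4 days per subject. Later SAEs judged possibly drug-related belong to it only if they enter the clinical database.

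The expected number of affected events is small and cannot be derived from the documents. The figure of 6.7 to 10 percentage points assumes that one such event occurs, in a subject with no other counted SAE. The conclusion also rests on reading 9.5.2 as written, with no implied end date. If the sponsor meant treatment-emergent SAEs throughout, what remains is a disclosure gap.

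**What to change.** In SAP 15.2, tabulate and list by SOC and PT all SAEs in the study database with onset after the first dose. Show the treatment-emergent subset (to 30 days after last dose) as a second column or a flag, so that the count now planned stays visible. Say in one sentence whether SAEs reported after follow-up are entered in the clinical database. Extending the fatal-event table in the same way is optional.

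If the restriction is kept, record it in SAP 20 as a change from protocol 9.5.2.

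The cost is one extra column and a few sentences, with no new data collection. The SAE count may rise slightly.

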15.3 Clinical Laboratory Variables

Due to COVID-19 PHE related disruptions, it is possible that some test results may be collected from a local laboratory. Local laboratory results and the associated normal ranges will be converted to SI units; local laboratory results, in SI units, will then be normalized to central lab ranges to be included in summary data analysis together with the central laboratory results. The normalization will be performed using the following scale transformation equation:

$$s = L_s + (x - L_x) \frac{U_s - L_s}{U_x - L_x}$$

where s is the normalized individual laboratory value to be used for summary; x is the original value from the local lab; L_x and U_x are the lower and upper limits from the local lab; L_s and U_s are the lower and upper limits from the central lab.

For labs with only a single upper (or lower) limit, the following scale transformation equation will be used:

$$s = x \frac{U_s}{U_x}$$

where s is the normalized individual laboratory value to be used for summary; x is the original value from the local lab; U_s is the upper (or lower) limit from the central lab; U_x is the upper (or lower) limit from the local laboratory. Local laboratory results and normalized results will be included in data listings. Only central lab and normalized local lab results will be used for summary of change from baseline, shift, and potentially clinically important (PCI) analyses.

Clinical laboratory assessments are performed according to the schedule presented in appendices (21.1 and 21.2).

- Clinical chemistry serum tests include the following:
 - Sodium (Na), potassium (K), chloride (Cl), phosphorus (P), calcium (Ca), magnesium (Mg), carbon dioxide (CO₂), blood urea nitrogen (BUN), creatinine (CR), uric acid
 - Mg will only be performed at Visit 1 (Screening)

- Alanine aminotransferase (ALT), aspartate aminotransferase (AST), gamma-glutamyl transpeptidase (GGT), alkaline phosphatase (ALP), total bilirubin (TBIL), lactate dehydrogenase (LDH)
- Glucose
- Albumin (ALB), total protein
- Thyroid stimulating hormone (TSH), free T3, and free T4
 - Thyroid function tests will be performed at Visit 1 (Screening)
- Hematology tests include the following:
 - Complete blood count (CBC) including:
 - White blood cell (WBC) count
 - Complete differential (relative and absolute)
 - Hematocrit (Hct), hemoglobin, red blood cells (RBC), platelets
 - Reticulocyte count
- Urinalysis tests include the following:
 - Blood, RBCs, WBCs, protein, glucose, ketones, specific gravity, pH

Clinical laboratory values (in Système International [SI] units) and the change from Baseline values will be summarized at each post-Baseline visit using descriptive statistics. The overall minimum, maximum as well as the last post-Baseline observed and change from Baseline values will also be summarized. For urinalysis with categorical results, the number and percentage of subjects will be tabulated by category at Baseline and each post-Baseline visit, and the denominator is the number of subjects with non-missing values for the given parameter and visit.

Laboratory values will also be summarized in shift tables to determine the number and percentage of subjects with values classified as below, within, and above normal ranges at each post-Baseline visit relative to the same classification at the Baseline visit. For the by-visit shift summary, the denominator is the number of subjects with non-missing values at Baseline and the given visit for the given parameter. For the shift to the overall post-Baseline minimum or maximum, all post-Baseline values will be considered, including unscheduled and out of window values and the denominator is the number of subjects with non-missing Baseline value and at least 1 post-Baseline value for the given parameter.

Clinical laboratory values are potentially clinically important (PCI) if they meet either the low or high PCI criteria listed in [Table 4](#) and [Table 5](#). The number and percentage of subjects with post-Baseline PCI values for each of the categories in Table 4 and Table 5 will be summarized

for selected parameters. For the overall post-Baseline summaries of PCI values, all post-Baseline values will be considered, including unscheduled and out of window values. Subjects with multiple PCI values for a given parameter will be counted only once for that parameter. For the overall post-Baseline summary, the numerator of the percentage is the number of subjects with at least 1 post-Baseline PCI laboratory value for the given parameter, and the denominator is the number of subjects with at least 1 post-Baseline laboratory value for the given parameter.

Table 4 Criteria for Potentially Clinically Important Laboratory Values – Hematology and Chemistry

Analyte	Conventional Unit	Low PCI Criteria	High PCI Criteria	SI Unit	Low PCI Criteria	High PCI Criteria
Hematology (whole blood)						
Hemoglobin (female)	g/dL	<10	>17	g/L	<100	>170
Hematocrit (female)	%	<30	>50	L/L	<0.3	>0.5
Leukocyte (White Blood Cell Count)	$\times 10^3/\mu\text{L}$	≤ 2.8	≥ 15	$\times 10^9/\text{L}$	≤ 2.8	≥ 15
Neutrophils	$\times 10^3/\mu\text{L}$	≤ 1.5	No upper limit	$\times 10^9/\text{L}$	≤ 1.5	No upper limit
Platelet Count	$\times 10^3/\mu\text{L}$	≤ 75	≥ 700	$\times 10^9/\text{L}$	≤ 75	≥ 700
Chemistry (serum or plasma)						
ALT (SGPT)	U/L	No lower limit	$\geq 3 \times \text{ULN}$	U/L	No lower limit	$\geq 3 \times \text{ULN}$
AST (SGOT)	U/L	No lower limit	$\geq 3 \times \text{ULN}$	U/L	No lower limit	$\geq 3 \times \text{ULN}$
Total Bilirubin	mg/dL	No lower limit	$\geq 1.5 \text{ ULN}$	umol/L	No lower limit	$\geq 1.5 \text{ ULN}$
BUN	mg/dL	No lower limit	≥ 30.0	mmol/L	No lower limit	≥ 10.71
Sodium	mEq/L	≤ 125	≥ 155	mmol/L	≤ 125	≥ 155
Potassium	mEq/L	≤ 3.0	≥ 5.5	mmol/L	≤ 3.0	≥ 5.5
Calcium, total	mg/dL	<8.0	>11.0	mmol/L	<2.0	>2.75
Lactate Dehydrogenase (LDH)	U/L	No lower limit	$\geq 3 \times \text{ULN}$	U/L	No lower limit	$\geq 3 \times \text{ULN}$
Alkaline Phosphatase	U/L	No lower limit	$\geq 3 \times \text{ULN}$	U/L	No lower limit	$\geq 3 \times \text{ULN}$
Uric acid (female)	mg/dL	No lower limit	≥ 8.5	umol/L	No lower limit	≥ 505.75
Albumin	g/dL	≤ 2.6	≥ 6.0	g/L	≤ 26	≥ 60
Total Protein	g/dL	≤ 5.0	≥ 10.0	g/L	≤ 50	≥ 100
Chloride	mEq/L	≤ 85	≥ 120	mmol/L	≤ 85	≥ 120
Glucose (random)	mg/dL	≤ 45.1	≥ 200.0	mmol/L	≤ 2.48	≥ 11
Serum Creatinine	mg/dL	Not Applicable	$>1.5 \text{ ULN}$	umol/L	Not Applicable	$>1.5 \text{ ULN}$
Gamma-Glutamyl Transferase (GGT)	U/L	Not Applicable	$\geq 3 \text{ ULN}$	U/L	Not Applicable	$\geq 3 \text{ ULN}$

Table 5 Criteria for Potentially Clinically Important Laboratory Values - Urinalysis

Urinalysis (qualitative dipstick)	Low PCI Criteria	High PCI Criteria
Blood (occult blood)	Not Applicable	\geq Moderate
Protein	Not Applicable	≥ 100 mg/dL
Glucose	Not Applicable	≥ 500 mg/dL

Clinical laboratory data will be displayed in data listings with date and study day of collection. All units will be displayed according to SI conventions for units. Out of range values will be flagged in the data listings (i.e., 'L' or 'H'). A separate listing will be provided for a subset of the chemistry, hematology, and urinalysis analytes with values classified as PCI.

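### SAP 15.3: where both reference limits are used and the lower/upper ratio differs between laboratories, normalising local results can change PCI flags near a ULN-multiple cut-off

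*SAP*

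**What the plan says.** SAP 15.3 foresees that, because of COVID-19 disruption, "it is possible that some test results may be collected from a local laboratory". The first step is stated as "Local laboratory results and the associated normal ranges will be converted to SI units". The result is then mapped to the central range by one of two formulas:

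- Two limits: s = Ls + (x − Lx)(Us − Ls)/(Ux − Lx), where x is the local result, Lx and Ux are the local limits, and Ls and Us are the central limits.
- One limit: s = x·Us/Ux. The SAP introduces it with "For labs with only a single upper (or lower) limit, the following scale transformation equation will be used".

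The normalised value then feeds all summaries: "Only central lab and normalized local lab results will be used for summary of change from baseline, shift, and potentially clinically important (PCI) analyses". On the criteria themselves the SAP says "Clinical laboratory values are potentially clinically important (PCI) if they meet either the low or high PCI criteria listed in" Tables 4 and 5. In Table 4, seven analytes have a criterion relative to ULN: ALT, AST, LDH, alkaline phosphatase and GGT at 3 times or more, total bilirubin at 1.5 times or more, and serum creatinine above 1.5 times. No separate rule is given for these criteria.

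Both values stay visible: "Local laboratory results and normalized results will be included in data listings". SAP 15.1 lists "Potentially clinically important changes in other safety assessments" among the primary safety endpoints.

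**The concern.** A ULN-multiple criterion asks how far a result lies above the upper limit, in units of that limit. The lower limit plays no part. The two-limit formula preserves something else: the position of the result relative to both limits. If the lower limit is a different fraction of the upper limit in the two laboratories, the multiple changes during normalisation, and the PCI decision is taken on the changed multiple.

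At stake is the count in the PCI table, which belongs to a listed primary safety endpoint. The separate listing of values classified as PCI could also omit or add a result, if that listing is driven by the normalised value. The SAP says this of PCI analyses but does not say it of the listing in so many words.

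**Working it through.** The plan states no figure to reproduce, so the check applies the two SAP formulas directly.

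**Inputs from SAP 15.3:** the two formulas, and the criteria m = 3 (five analytes) and m = 1.5 (two analytes). **Assumed:** every reference limit, since the documents give none.

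**Effect on the multiple.** Write k = x/Ux for the local multiple, a = Lx/Ux for the local ratio and b = Ls/Us for the central ratio. Dividing the two-limit formula by Us gives

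s/Us = 1 + (k − 1)(1 − b)/(1 − a).

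For k other than 1 this equals k only if a = b. Lower limits of 0 in both laboratories are a special case of a = b. The single-limit formula gives s/Us = k for any pair of limits.

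**Range status.** The two-limit formula is increasing and sends Lx to Ls and Ux to Us. Below, within and above range are therefore preserved, and the shift tables do not change.

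**Trigger point.** Setting s/Us = m gives the local multiple at which the flag switches:

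k = 1 + (m − 1)(1 − a)/(1 − b).

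| Criterion m | Local ratio a | Central ratio b | Calculation | Local trigger |
|---|---|---|---|---|
| 3 | 0.25 | 0.20 | 1 + 2 × 0.75/0.80 | 2.88 |
| 3 | 0.20 | 0.25 | 1 + 2 × 0.80/0.75 | 3.13 |
| 1.5 | 0.55 | 0.50 | 1 + 0.5 × 0.45/0.50 | 1.45 |
| 1.5 | 0.50 | 0.55 | 1 + 0.5 × 0.50/0.45 | 1.56 |

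A wider assumed gap moves the trigger further. For m = 3, ratios of 0.30 (local) and 0.10 (central) give 1 + 2 × 0.70/0.90 = 2.56. The reverse gives 1 + 2 × 0.90/0.70 = 3.57. Equal ratios give exactly m.

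**Examples with the same ULN of 40 in both laboratories.** The limits are assumed, and the values were chosen to fall between the two triggers.

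- ALT 122, local range 8–40: 122/40 = 3.05. On central 10–40, s = 10 + 114 × 30/32 = 116.9, which is 2.92 times ULN. The flag is missed.
- ALT 117, local range 10–40: 117/40 = 2.93. On central 8–40, s = 8 + 107 × 32/30 = 122.1, which is 3.05 times ULN. The flag is falsely raised.
- Creatinine 62 µmol/L, local range 20–40: 62/40 = 1.55. On central 24–40, s = 24 + 42 × 16/20 = 57.6, which is 1.44 times ULN. The flag is missed.
- Creatinine 58 µmol/L, local range 24–40: 58/40 = 1.45. On central 20–40, s = 20 + 34 × 20/16 = 62.5, which is 1.56 times ULN. The flag is falsely raised.

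Under the single-limit formula the first result stays at 122 × 40/40 = 122, or 3.05 times ULN, and is flagged. The SAP's two formulas thus give opposite answers for the same result and the same ULN.

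**The case against.** The strongest reply is that the SAP deliberately uses one harmonised value for change, shift and PCI, so that those outputs agree. Table 4 does not say whose ULN is meant, so calling a flag missed presumes that the reporting laboratory's multiple is the standard. The equal-ULN examples answer this. A result of 122 against an upper limit of 40 is 3.05 times ULN in either laboratory, yet it is not flagged, and only the lower limits caused that. Harmonisation remains a fair argument for absolute cut-offs, and no objection is made to it there.

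Other parts of the reply stand. A changed flag needs a post-Baseline local result, the two-limit formula, unequal ratios, and a value between the true and shifted triggers. It must also fall in one of the parameters selected for PCI tabulation, which SAP 15.3 does not name. Protocol 4.2 excludes girls with raised transaminases, bilirubin or creatinine at Screening beyond its stated limits. All analyses are descriptive (Protocol 9.2), and with 10 to 15 subjects a discordant case can be found by hand in the listings.

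A reader might infer that every local result for all seven analytes is misjudged. The documents do not support that. They do not show which analytes have two-limit ranges or whether any ratio differs, so seven is an upper bound. Nor can the single-limit formula be assumed for all seven because Table 4 shows no low criterion for them: that column describes the PCI criterion, not the reference range.

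**Conclusion.** The point holds conditionally and is minor. For up to seven analytes, where both limits are used and the lower/upper ratio differs between the local and central laboratories, a PCI flag near the cut-off can be wrong in either direction.

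The size is illustrative, because every range is assumed. How many results are affected is unknown and may be zero. If one subject's status did change, the PCI percentage for that parameter would move by 1/15 to 1/10, about 7 to 10 percentage points, provided that all 10 to 15 planned subjects have a post-Baseline value.

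A subject who already meets the criterion on another value does not change the PCI table, which counts each subject once per parameter. The listing of PCI values could still lose or gain the individual result if it uses the normalised value.

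It would go too far to conclude that the shift tables or the safety endpoint as a whole are unreliable. Range status is preserved, and the local values remain listed.

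**What to change.** Add one sentence to SAP 15.3: *For PCI criteria expressed as a multiple of ULN, local results will be classified by the unnormalised value divided by the reporting laboratory's ULN (equivalently s = x·Us/Ux).* This extends the SAP's own single-limit ratio to the seven criteria. In the examples it gives 3.05 and 1.55 (flagged) and 2.93 and 1.45 (not flagged), whatever the lower limits.

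Keep the existing normalisation for change from Baseline, shift tables and absolute PCI cut-offs.

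The cost is that sentence, a small programming change and one footnote. No new data are needed, because the normalisation already requires the local values and ranges. There is one drawback. The SAP also plans that "The overall minimum, maximum as well as the last post-Baseline observed and change from Baseline values will also be summarized", and those summaries stay on the two-limit value. The PCI flag and the summarised maximum can then disagree for the same local result, and the PCI table footnote should say so.

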2.1.1 Primary Endpoints

The safety endpoints are as follows:

- treatment-emergent adverse events (TEAEs)
- serious adverse events (SAEs)
- withdrawals due to adverse events (AEs)
- potentially clinically important changes in other safety assessments

The pharmacokinetic (PK) endpoints are as follows:

- whole blood concentration of trofinetide
- trofinetide PK parameters using the population PK approach

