- Observed: ≤450, 451 - ≤480, 481 - ≤500, and >500; >450; >480.
- Change from Baseline: ≤10, 11 – 30, 31 – 60, and >60; >30.

For cardiologist's interpretations, the number and percentage of subjects with ECG results that are determined as normal or abnormal will be summarized at scheduled visits. The overall post-baseline worst interpretation will also be summarized (i.e. if a subject has one or more post-baseline ECG results that is/are considered as abnormal, this subject will be counted in the abnormal category). Cardiologist's interpretations will also be summarized in a shift table. The shifts from Baseline to overall post-Baseline worst interpretation will also be presented. For the by-visit shift summary, the denominator is the number of subjects with non-missing cardiologist's interpretation at Baseline and the given visit. For the summaries of shift from Baseline to the overall post-Baseline worst interpretation, the denominator is the number of subjects with non-missing Baseline and at least 1 post-Baseline cardiologist's interpretation.

Electrocardiogram variable values will be considered PCI if they meet the criteria listed in Table 7. The number and percentage of subjects with post-baseline PCI values will be presented at each post-Baseline visit and for overall post-Baseline. For the by-visit summary, the numerator for the percentage is the number of subjects with a post-Baseline PCI ECG for the given parameter and visit, and the denominator is the number of subjects with non-missing values for the given parameter and visit. For the overall post-Baseline summary, the numerator for the percentage is the number of subjects with at least 1 post-Baseline PCI ECG for the given parameter, and the denominator is the number of subjects with at least 1 post-Baseline ECG value for the given parameter. A listing of all subjects with any PCI ECG values will be provided.

Table 7 Criteria for Potentially Clinically Important ECG Values

ECG Parameter	Unit	High PCI Criteria
QRS Interval	msec	≥120
PR Interval	msec	≥220
QTcB	msec	>500
QTcF	msec	>500
QTcB: change from baseline		>60 msec
QTcF: change from baseline		>60 msec

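### The laboratory PCI count and three ECG rows ignore Baseline, although the primary safety endpoint is potentially clinically important (PCI) changes

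*SAP*

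**What the plan says.** Protocol 2.1.1 lists among the primary safety endpoints "potentially clinically important changes in other safety assessments", and SAP 15.1 repeats it. The summaries that deliver this endpoint differ by type of assessment.

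- **Laboratory (SAP 15.3).** A value is PCI once it passes a low or high limit in Tables 4 and 5. In the overall count, "the numerator of the percentage is the number of subjects with at least 1 post-Baseline PCI laboratory value for the given parameter". The denominator is every girl who has any result after Baseline for that analyte. The summary covers selected parameters, which the SAP does not name.
- **ECG (SAP 15.5).** The overall rule has the same form: "the numerator for the percentage is the number of subjects with at least 1 post-Baseline PCI ECG for the given parameter". Its denominator is every girl who has any ECG result after Baseline for that parameter. Table 7 has six rows. Four are limits on the observed value (QRS ≥120, PR ≥220, QTcB >500, QTcF >500 msec). Two are changes of more than 60 msec, one for QTcB and one headed "QTcF: change from baseline".
- **Vital signs (SAP 15.4).** All four parameters in Table 6 carry a change-from-Baseline condition, and the overall denominator requires a Baseline value.

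SAP 5.5 defines Baseline as the last non-missing assessment before the first dose.

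**The concern.** The endpoint is a change, but the laboratory rule and three of the ECG rows count a state. A girl whose value was already past the limit before dosing, and is past it at any later sample, enters the numerator exactly as a girl who crossed the limit on treatment does.

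This matters more here than in a controlled trial. There is one arm and no hypothesis test (Protocol 9.2), so each girl's own Baseline is the only comparator. With 10 to 15 girls, a single pre-existing case visibly moves a percentage. SAP 17 sends the same analyses into an interim report for a New Drug Application, where a reader would naturally take the PCI table as a table of changes on treatment.

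**Working it through.** The documents state no PCI rate or event count, so there is no figure to reproduce. The check is of the rule, row by row, followed by simple arithmetic.

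**1. Laboratory criteria with a Baseline term.** Table 4 has 5 hematology and 16 chemistry analytes; Table 5 has 3 urinalysis tests: 5 + 16 + 3 = 24. Counting low and high limits separately gives 9 for hematology, 23 for chemistry and 3 for urinalysis: 9 + 23 + 3 = 35. None of the 35 refers to Baseline.

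**2. What the entry criteria remove.** Exclusion 8 (Protocol 4.2) bears on 6 of the 35: low hemoglobin, high ALT, high AST, high bilirubin, high creatinine and low potassium. The other 35 − 6 = 29 have no named limit; examples are high potassium, white cells, neutrophils, platelets, glucose and LDH. Exclusion 9 removes a laboratory value judged clinically significant, for any analyte. Both apply at Screening, which can last up to 4 weeks before Baseline.

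**3. What the other laboratory outputs show.** The shift tables use Baseline, but with classes below, within and above the normal range. A girl above normal both before and after dosing shows no shift, and the table cannot say whether her Baseline value had already passed the PCI limit. Categorical urinalysis is tabulated at Baseline and at each visit, but as separate counts, not as shifts within a girl.

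**4. ECG rows.** Two of the six already measure change. A third, QTcF >500, cannot pre-exist in an eligible girl, because exclusion 11a removes QTcF >450 ms at Screening or Baseline. That leaves 6 − 2 − 1 = 3 rows: QRS, PR and QTcB >500. Exclusion 11d (other clinically significant ECG findings, at Screening or Baseline) narrows these further, by judgement.

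QTcB >500 can coexist with an eligible QTcF. The two corrections differ by the factor QTcB/QTcF = RR^(−1/6). With QTcF at most 450, QTcB >500 needs RR < (450/500)^6 = 0.531 s, a heart rate above 60/0.531 ≈ 113 bpm. That is below the SAP's own high-pulse limit of 131 bpm in Table 6.

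**5. Weight of one pre-existing case.** This is 1/n: 1/15 = 6.7 and 1/10 = 10.0 percentage points. The table compares the planned rule with one that counts only girls who were not PCI at Baseline.

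| Girls | PCI at Baseline and again later | New cases | Planned rule | Treatment-emergent |
|---|---|---|---|---|
| 10 | 1 | 0 | 1/10 = 10.0% | 0/9 = 0% |
| 10 | 1 | 1 | 2/10 = 20.0% | 1/9 = 11.1% |
| 15 | 1 | 0 | 1/15 = 6.7% | 0/14 = 0% |
| 15 | 1 | 1 | 2/15 = 13.3% | 1/14 = 7.1% |

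**6. How likely is such a girl?** The documents give no Baseline PCI prevalence p, so p is an assumption. The chance that at least one girl is PCI at Baseline on one parameter is 1 − (1 − p)^n.

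| Assumed p | n = 10 | n = 15 |
|---|---|---|
| 1% | 9.6% | 14.0% |
| 5% | 40.1% | 53.7% |
| 10% | 65.1% | 79.4% |

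For a given p, these are upper limits on the chance of a pre-existing case entering the count, because the girl must also be PCI after Baseline.

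**The case against.** The strongest reply is that nothing is lost and the rule errs on the cautious side. All data are listed, PCI laboratory values for a subset of analytes get their own listing, and 10 to 15 girls can be checked one by one. Changes from Baseline are summarized by visit and for the overall minimum and maximum. Protocol 9.5.2 leaves safety details to the SAP, and the protocol never defines a PCI change. Counting every post-Baseline PCI value also keeps a girl who starts PCI and worsens, whom a purely treatment-emergent count would drop.

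Much of this stands. It makes the problem one of counting and labelling, and it is the reason to keep the planned count. It does not make a table of post-Baseline states a table of changes.

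The shift tables also do more than they might seem to. For the seven analytes whose limits are multiples of the upper limit of normal (ALT, AST, bilirubin, LDH, alkaline phosphatase, creatinine, GGT), if no girl is above normal at Baseline then none is PCI there. The tables can thus rule the problem out for those analytes, but cannot identify who was PCI when someone was above normal.

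A reader might infer that the whole ECG summary ignores Baseline. It does not: three of the six rows are safe, for the reasons in step 4. A reader might also infer that any Baseline abnormality becomes a case. It does so only if a later value also meets the limit; one that has resolved by the first post-Baseline sample is not counted.

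**Conclusion.** The point holds for the summarized laboratory parameters and for the QRS, PR and QTcB >500 rows. There the planned count does not measure the stated endpoint, and it is inconsistent with the SAP's own handling of vital signs. The size is 6.7 (n = 15) to 10 (n = 10) percentage points per parameter for each girl who is PCI both before and after the first dose.

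That size assumes every enrolled girl has a post-Baseline value for the parameter. How often it occurs is unknown: the range in step 6 rests wholly on an assumed prevalence of 1% to 10%. It is tempting to conclude that the PCI rates are overstated, or that they cannot be interpreted. The documents support neither. They give no Baseline rate, so overstatement is possible but not shown, and the listings allow individual cases to be traced. This is a change worth making, not a threat to the study.

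**What to change.** For the summarized laboratory parameters in SAP 15.3, and for the QRS, PR and QTcB >500 rows in SAP 15.5, keep the planned any-post-Baseline count and add two items beside it:

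1. The number of girls who are PCI at Baseline, by the SAP 5.5 definition.
2. A treatment-emergent PCI count. The numerator is girls with a post-Baseline PCI value who were not PCI in the same direction at Baseline. The denominator is girls with a Baseline value that is non-PCI for that criterion and at least one post-Baseline value.

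The other three Table 7 rows and the vital-sign criteria need no change.

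The cost is SAP wording and a little more programming. No new data are needed, since laboratory tests, urinalysis and ECGs are already scheduled before dosing. The added line has a slightly smaller denominator. A girl who is PCI at Baseline and worsens leaves that line but stays visible in the planned count and in the listings.
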